4.2 Exclusion Criteria

4.2.1 Any treatment for the bladder tumor other than intravesical therapy between the pre-study cystoscopy or radiologic imaging which identified the suspected bladder tumor and the scheduled surgical removal or cystoscopy-guided biopsy of that tumor.

4.2.2 Any chemotherapy and/or radiation therapy received ≤ 3 months of study entry and any immunotherapy received ≤ 6 months of study entry (with the exception of BCG treatment).

4.2.2.1 Any prior external beam radiation to the pelvis.

4.2.3 A concurrent skin rash or skin condition requiring treatment with a prescription medication.

4.2.4 The following medications may not be taken within 24 hours of the first dose of study agent or at any time while a participant is taking study agent due to the risk of significant drug-drug interaction.

- Coumadin
- Strong CYP3A4 inhibitors (which lead to decreased erlotinib metabolism/increased erlotinib levels) including ketoconazole, atazanavir, boceprevir, ceritinib, clarithromycin, cobicistat, darunavir, dasabuvir, idelalisib, indinavir, itraconazole, lopinavir, nefazodone, nelfinavir, ombitasvir, paritaprevir, posaconazole, ritonavir, saquinavir, telaprevir, telithromycin, troleandomycin, voriconazole, and grapefruit or grapefruit juice.
- CYP3A4 inducers (which lead to increased erlotinib metabolism/decreased erlotinib levels) including rifampicin, rifabutin, rifapentine, phenytoin, carbamazepine, phenobarbital, primidone, enzalutamide, fosphenytoin, lumacaftor, mitotane, and St. John's Wort.
- Agents which decrease gastric acid are allowed but should be avoided if possible.
- Participants may resume inhibitors or inducers of CYP3A4 > 14 days after their last dose of study agent

4.2.5 Participants requiring daily use of non-steroidal anti-inflammatory drugs (NSAIDs), with the exception of ≤ 81 mg aspirin per day. During study participation, acetaminophen is preferred for treatment of pain; the use of NSAIDs, as needed for pain, is discouraged.

4.2.6 Participants may not be receiving any other investigational agents.

4.2.7 History of allergic reactions attributed to compounds of similar chemical or biologic composition to erlotinib or clindamycin (topical agent for potential skin toxicity).

4.2.8 An underlying predisposition to rectal or gastrointestinal bleeding or uncontrolled intercurrent illness including, but not limited to, ongoing or active infection, symptomatic congestive heart failure, unstable angina pectoris, uncontrolled cardiac arrhythmia, or psychiatric illness/social situations that would limit compliance with study requirements.

4.2.9 Females who are pregnant or lactating may not participate in this study. Females of child-bearing potential must have a negative pregnancy test before starting study agent. Patients who have had a bilateral oophorectomy, hysterectomy, or are greater than 1 year since their last menses are not considered to be of child-bearing potential.

4.3 Inclusion of Women and Minorities

Both men and women and members of all races and ethnic groups are eligible for this trial. Because of the demographics and incidence history at our consortium sites we expect a predominance of white males, which reflects the incidence of bladder cancer. The University of Wisconsin Chemoprevention consortium sites see an average of 76% male patients and 89% white patients. However, many of our consortium sites serve ethnically diverse areas. Urology San Antonio has shown successful recruitment with Hispanic and Latino patients (25% of diagnoses, 49.1% of the population), and Johns Hopkins University serves communities that are much more diverse with populations between 25-40% African-American. Johns Hopkins University and the Carolina Urologic Research Center of Myrtle Beach, SC both of which serve a more diverse patient population are recent additions to the Consortium. The Carolina Urologic Research Center has one of the largest bladder cancer populations in the country.

The UWCCC continues to look for innovative ways to increase the minority participation in our own clinical trials, despite the demographic profile of our community. This is the focus of several initiatives of the UWCCC Cancer Control Program. In addition to devising more effective means of reaching local minority populations, the UWCCC's affiliate minority recruitment has been strengthened through affiliated research networks, examples being the Wisconsin Oncology Network or the Wisconsin Network for Health Research (both started by the Consortium PI/[name]) which includes multiple clinical sites in Milwaukee county where underserved populations approach 20% compared to <10% in UWCCC's catchment area. Another underserved population that our affiliated research networks help with is the rural poor and the elderly poor. This is especially true with the Wisconsin Network for Health Research which has many clinic sites in rural defined areas with median incomes at or near the poverty line. In addition, the UWCCC has multiple ongoing initiatives to encourage underrepresented communities participation in health care research including efforts by Study PI/Chair, [name], who performs monthly outreach to local African-American churches for cancer and clinical research awareness.

4.4 Recruitment and Retention Plan

In an attempt to address participant concerns about extra visits, missed work, and transportation expenses, we have minimized the number of study visits in this protocol. After the consent form is signed, all baseline/screening procedures and examinations will be done at one visit, including research blood sample collection (Urine sample collection will be collected only as pregnancy test option for women of child bearing potential). Participants found to be screen failures, will not be randomized and the research samples will be destroyed on-site. Eligible participants will have two additional study visits, one at Day 8* and one on the day of their surgery.

*The Day 8 clinic visit is optional; a Day 8 phone contact will be required if clinic visit doesn't occur

Study brochures, posters, protocol fast fact sheets, pocket cards, and other recruitment materials will be developed at the CLO (Consortium Lead Organization, University of Wisconsin) and made available to the participating sites for use or modification. The CLO will coordinate with the other sites to develop comprehensive site-specific recruitment plans.

5. AGENT ADMINISTRATION

Intervention will be administered on an outpatient basis. Reported adverse events (AEs) and potential risks are described in Section 6.2.

5.1 Dose Regimen and Dose Groups

There will be two treatment groups for this trial:

Treatment Group 1) Active study agent erlotinib 600 mg administered as four 150 mg tablets by mouth once weekly for 3 doses. (30 participants)

Treatment Group 2) Placebo as administered as 4 placebo tablets by mouth weekly for 3 doses (15 participants)

Randomization to each treatment group will be stratified by planned surgery (TURBT vs. cystectomy) and planned use of agents that significantly decrease erlotinib bioavailability. For this study this is defined as tobacco use (current smoker) or daily scheduled use of proton pump inhibitors. A smoker is defined as an individual who has smoked ≥ 100 cigarettes in their lifetime and who currently smokes ≥ 1 cigarette per day).

5.2 Study Agent Administration

The study agent (erlotinib or placebo) will be dispensed by an investigational pharmacist or appropriate study staff at the participating organization (PO) and then self-administered by the participant at home. A single bottle containing 16 tablets of study agent will be dispensed. If the participant is unable to return to the institution to pick up their study agent, the agent will be mailed to them via courier.

The study agent must be taken on an empty stomach (at least two hours after last eating). After taking their dose of study agent the participant must wait an hour before eating anything.

On Day 1, the participant will take one dose, 600 mg erlotinib or placebo in the form of four 150 mg erlotinib or matching placebo tablets by mouth in the evening (unless otherwise directed) on an empty stomach. All 4 tablets comprising a single dose of study agent will be taken together at the same time.

On Day 8, the participant will take their second dose of study agent (600 mg erlotinib or placebo in the form of four 150 mg erlotinib or matching placebo tablets) on an empty stomach as instructed either in the clinic following the collection of blood samples for pharmacokinetics or at home. Prior to the Day 8 Optional Visit/Mandatory Safety Assessment Phone call, the participant will receive a reminder phone contact instructing the participant when to take the Day 8 dose.

On Day 15 the participant will take their third dose of study agent approximately 9-18 hours before their scheduled surgery (600 mg erlotinib or placebo in the form of four 150 mg erlotinib or matching placebo tablets). The participant will receive a reminder phone contact prior to their final study dosing day instructing them when to take this final dose.

If surgery is delayed beyond the 16th day but less than the 23rd day, delay administration of the third dose until approximately 9-18 hours prior to the surgery. If surgery is delayed to day 23 through day 28, administer the third dose at day 15, and the fourth dose approximately 9-18 hours before surgery. If

surgery is delayed beyond day 28 (four weekly study drug doses), the patient will be considered not evaluable for the primary endpoint.

5.2.1 Supportive Medications

All study subjects will receive, along with study medication, 30 gm tube of topical Clindamycin (1%) gel and a 30 gm tube of topical Hydrocortisone (1%) cream. They will be instructed that at the first signs of painful or red acneiform skin lesions to apply twice daily (AM and PM) topical clindamycin to the aforementioned concerning skin lesions. If these lesions do not improve (less redness or pain) they will be instructed to also start applying topical hydrocortisone twice daily (AM and PM) at time points two hours apart from application of topical clindamycin. If red or painful skin lesions continue or worsen, study participants will be instructed to call study personnel to both report the toxicity and receive additional instructions. Examples of additional instructions include increased frequency of topical application, consideration of systemic antibiotics, avoiding alcohol-based skin products, etc.

Subjects should be directed that if they experience diarrhea likely to be attributable to study drug they should use loperamide (Imodium) 2 mg (1 dose) with the first loose, watery stool, and with each watery stool thereafter. If the patient has 3-4 watery stools per day, they should contact their research doctor or coordinator.

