Participants for this protocol will be accrued from a population of males and females 18 years of age and older who have a confirmed or suspected bladder tumor which will be treated with TURBT (or planned cystoscopy with biopsies) or cystectomy (total or partial). Eligible participants will be randomly assigned to either 600 mg erlotinib PO or matching placebo once weekly for 3 doses preceding their scheduled bladder surgery. The study will be terminated when all participants have completed study dosing, their scheduled surgical treatment, and a 7-14 day post-surgery follow-up period.

There is no run-in period specified for this protocol. Potential study participants will be identified from the population of patients being evaluated and treated for bladder tumors at each of the participating institutions. After being presented with information about the protocol, patients interested in participating will be scheduled for a screening/baseline study visit. After completion of the informed consent process, the following assessments/procedures will be conducted:

Screening/Baseline visit (within 30 days of first dose of study agent):

- eligibility assessment
- medical/surgical history and baseline symptoms
- physical exam/vital signs (including performance status assessment)
- clinical safety labs (including pregnancy testing for females of childbearing potential)
- plasma pharmacokinetics
- request for randomization
- International Prostate Symptom Score (I-PSS)

Study agent and topical ointment (topical clindamycin, topical hydrocortisone) dispensing: (within 30 days of baseline assessments) either in clinic or study agent will be mailed to the participant via overnight courier with a phone contact prior to dosing. Ointment instructions will be included (See Appendix B).

- study agent dosing instructions
- ointment instructions
- concomitant medication review and adverse event assessment

Pre Day 8 Phone contact (approximately 24-72 hours prior to Day 8 Visit):

- instruct participant on dose and time of Day 8 study drug administration

Day 8 Visit*:

- physical exam/vital signs (including complete assessment of any rash per CTCAE criteria)
- clinical safety labs
- plasma pharmacokinetics
- Day 8 Study dosing after plasma pharmacokinetics
- concomitant medication review, compliance and adverse event assessment

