5.6 Dose Modification

Study drug will be dose reduced (by 50%) from 4 tablets to 2 tablets for any of the following events:

- A grade 1 rash or diarrhea that the study subject finds unacceptable and desires the 50% dose reduction.
- A grade 2 skin toxicity
- A grade 2 diarrhea that does not respond to Imodium
- Any toxicity or adverse event \geq grade 3
- MD discretion for side effects assessed as at least possibly related to the study drug and for which the study subject finds unacceptable and desires the 50% dose reduction

Subjects that meet the above dose modification criteria even after a dose reduction will not receive any further doses. At the first report of grade 1 or 2 skin toxicity, subjects should be instructed on using the dispensed topical ointments (1% Clindamycin, 1% hydrocortisone): apply twice daily (not at the same time) each ointment to the affected area only. Subjects who report grade 1 or 2 diarrhea likely to be attributable to study drug should be instructed to use loperamide (Imodium) 2 mg after each loose stool. Provide participants with a copy of Appendix B.

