7. CLINICAL EVALUATIONS AND PROCEDURES

7.1 Schedule of Events

Evaluation/ Procedure	Pre-Study Evaluation/ Baseline (≤30 days)	Randomize / Dispense Study Agent	Phone Contact (24-72 hours Prior to Day 8 Visit)	Day 8 Visit ⁷	Pre-surgery phone contact (24- 72 hours prior to surgery)	Surgery Visit (day 15-16)	Post-surgery Phone Contact (7- 14 days after surgery)
Informed Consent	X						
Assess Eligibility	X						
Medical History	X						
Physical Exam	X ²			X ²		X ²	
Baseline Symptoms	X						
Vital signs (temp, pulse, BP, Ht and Wt)	X			X		X	
Hgb, Hct, WBC, Plt	X			X		X	
Na, K, CO ₂ , Cl	X			X		X	
BUN,Creat	X			X		X	
AST, ALT, Alk Phos	X			X		X	
T Bili	X			X		X	
Urine or Serum Pregnancy Test	X						
Blood for PK	X			X		X	
Tissue Blocks/slides						X	
Concomitant Meds	X			X ⁷		X	X
Dose of study agent		X ¹		X ³	X ^{4,5}		
Dose reminder call			X		X		
Dispense 1% clindamycin & 1% hydrocortisone		X ⁶					
I-PSS (men only)	X					X	
Compliance				X ⁷		X	
Adverse Events				X ⁷		X	X

- The date of the Day 1 dose equals the date of the surgery minus 15 days. For example, if the surgery was on the 23rd of the month, 23-15= 8, therefore the participant would take their 1st dose of study agent on the 8th of the month.
- Physical exam should include evaluation for rash. If a rash is noted, document the extent of the rash per CTCAE grading criteria
- The Day 8 dose of study agent should be taken during the clinic visit after the pharmacokinetic blood draw is completed or at home as instructed by study staff.
- The pre-surgical dose of study agent should be taken in the evening prior to the day of surgery and within approximately 9-18 hours of the time of the pre-surgery pharmacokinetic blood draw.
- If surgery is delayed beyond the 16th day but less than the 23rd day, delay administration of the third dose until the evening prior to the day of surgery. If surgery is delayed to day 23 through day 28, administer the third dose at day 15 and the fourth dose in the evening prior to day of scheduled surgery. If surgery is delayed beyond day 28 (four weekly study drug doses), the patient will be considered not evaluable for the primary endpoint. A reminder phone contact should be made 72 – 24 hours prior to the day of the re-scheduled surgery.

6. Dispense to all study participants when dispensing medication per NCI requirements. Instruct participant to use these agents for skin toxicities.

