APPENDIX B

Information on Erlotinib (Study Drug)

Erlotinib
(Tarceva)

Description

Erlotinib is a medication used in the treatment of some cancers. This study is being done to determine the potential cancer prevention effects in bladder tissue when erlotinib is taken once a week, and to determine how well people tolerate taking erlotinib once a week. Erlotinib needs to be taken on an empty stomach, which means taking it at least 2 hours after you last ate something one hour before you next eat something.

How It Is Given

This medicine is a pill that you swallow.

When to call us: We would like to know if you experience any rash or diarrhea that continues for over 24 hours. We would also like to know if you experience any unexplained, persistent cough, fever, or shortness of breath immediately.

Common Side Effects When Taken Daily:

COMMON, SOME MAY BE SERIOUS In 100 people receiving erlotinib, more than 20 may have:

• Rash• Diarrhea• Loss of appetite• Tiredness or fatigue• Shortness of breath• Cough• Nausea• Infection• Vomiting

OCCASIONAL, SOME MAY BE SERIOUS

In 100 people receiving erlotinib, from 4 to 20 may have:

- Sores in mouth
- Itching
- Acne
- Dry skin
- Weight loss
- Irritation (redness, swelling, warmth, and pain) or infection of the skin around fingernails or toenails
- Eye infection/pink eye
- Dry eyes
- Stomach pain or pain in the abdomen (belly)
- Red bumps on the skin that are red, sore, and possibly infected

POSSIBLE, SOME MAY BE SERIOUS

The frequency of some individual side effects for people receiving erlotinib has not yet been determined:

- Shoulder pain
- Change in urine color
- Indigestion
- Gas in the belly, burping
- Irritability (easily annoyed or made angry)
- Swelling of the face, hands, feet or ankles
- Runny nose
- Dizziness
- Headache
- Blood clot in the lung which may cause pain, shortness of breath
- Stroke (Stoppage of blood flow to your brain which may cause paralysis, weakness, headache)
- Death or injury to unborn baby
- Because of the potential harm to the infant, women should be advised against breast-feeding while receiving erlotinib therapy

RARE, SOME MAY BE SERIOUS

In 100 people receiving erlotinib, 3 or fewer may have:

Although very rare, some of the side effects listed below can cause death

- Abnormal laboratory result which may indicate liver damage
- Liver damage
- Kidney damage which may cause swelling, may require dialysis

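### Sections 5.2.1 and 5.6 differ on when hydrocortisone starts for an untreated rash, and Appendix B, cited for ointment instructions, has no ointment or loperamide directions and a different diarrhea call trigger

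*Combined protocol and SAP*

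**What the plan says.** **Rash.** Section 5.2.1 gives every participant a tube of 1% clindamycin gel and a tube of 1% hydrocortisone cream. Clindamycin is applied twice daily when lesions first appear. Hydrocortisone is conditional: "If these lesions do not improve (less redness or pain) they will be instructed to also start applying topical hydrocortisone twice daily", two hours apart from the clindamycin. Participants call study personnel if lesions persist or worsen.

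Section 5.6 is worded differently: "At the first report of grade 1 or 2 skin toxicity, subjects should be instructed on using the dispensed topical ointments", followed by "apply twice daily (not at the same time) each ointment to the affected area only". It does not require that clindamycin has been tried first. Note 6 to the schedule of events in Section 7.1 says only "Instruct participant to use these agents for skin toxicities".

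**Participant sheet.** Section 3, on dispensing, says "Ointment instructions will be included (See Appendix B". Section 5.6 closes its ointment and loperamide directions by saying that participants with grade 1 or 2 diarrhea "should be instructed to use loperamide (Imodium) 2 mg after each loose stool. Provide participants with a copy of Appendix B".

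**When to call about diarrhea.** Section 5.2.1 directs 2 mg of loperamide with each watery stool and adds: "If the patient has 3-4 watery stools per day, they should contact their research doctor or coordinator". Appendix B says: "We would like to know if you experience any rash or diarrhea that continues for over 24 hours".

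**The concern.** Two sections give different regimens for the same event, and the handout that should carry the directions does not. Six sites will work from this text. One site could start hydrocortisone at the first report of a rash while another holds it back.

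The sheet matters because contact is limited. Section 3 allows study agent to be mailed, with a phone contact before dosing. The Day 8 clinic visit is optional, and the call that replaces it comes after the Day 8 dose (Section 7.3). Section 8.2 reports that in the weekly high-dose lung cancer study diarrhea usually began within 24 to 48 hours of a dose and was well controlled by as-needed loperamide. After the Day 1 dose that window closes around Day 3. The next scheduled contact is the reminder call 24 to 72 hours before Day 8, about Day 5 to Day 7. Section 5.2.1 lists only the two tubes as dispensed, so participants must obtain loperamide themselves. Section 5.6 also makes one dose-reduction criterion depend on grade 2 diarrhea failing to respond to Imodium, which presumes that participants knew to take it.

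**Working it through.** The plan states no figure to reproduce. The check sets the texts side by side and counts what each directs.

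**1. Rash reported before any treatment**

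| Source | Clindamycin per day | Hydrocortisone per day | Total |
|---|---|---|---|
| Section 5.2.1, first step | 2 | 0 | 2 |
| Section 5.6, first report | 2 | 2 | 4 |

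Section 5.2.1 sets no time for judging that lesions have not improved, so the length of the difference cannot be computed. For a participant who has already used clindamycin without improvement, 5.2.1 also gives 2 + 2 = 4, and the sections largely agree. Note 6 in Section 7.1 gives no order, so it does not settle the conflict.

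**2. Contents of Appendix B**

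The sheet covers a description of erlotinib, how it is given, when to call, side effects and drug interactions. It does not mention clindamycin, hydrocortisone, an ointment or loperamide. The nearest term is corticosteroids, listed as a risk factor for stomach perforation. Directions present: 0 of 3. Appendix B runs straight into Appendix C, and no page was removed between them, so this is not a gap in the published copy. Both tubes go to all 15 + 30 = 45 planned participants.

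The two defects interact. The sheet asks for a call when a rash lasts over 24 hours but never says to start clindamycin. A participant relying on it would make exactly the untreated-rash report on which 5.2.1 and 5.6 disagree.

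**3. Diarrhea**

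- Loperamide directed by the time the 5.2.1 call trigger is reached: 3 stools × 2 mg = 6 mg, or 4 stools × 2 mg = 8 mg. Appendix B directs 0 mg.
- Let *t* be the hours from onset to 3-4 watery stools, with *t* under 24. If diarrhea persists, the sheet's call comes later by 24 − *t* hours. The documents give no value for *t*. Assumed examples: *t* = 6 gives 24 − 6 = 18 hours; *t* = 12 gives 24 − 12 = 12 hours. The delay is always under 24 hours.
- If frequent diarrhea stops within 24 hours, the sheet prompts no call.
- If stools are fewer but last over 24 hours, the sheet prompts the earlier call.

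**The case against.** The best reply is that the sheet is not the protocol's only channel. Ointment instructions are a listed dispensing task in Section 3, Section 5.2.1 requires participants to be told about both ointments and loperamide, and Section 7.1 repeats the ointment instruction. A call to staff would bring the 5.6 directions. Other written material may exist: the consent pages are not in the public copy, and Section 6.8 refers to Study Visit Guides that are not included. All of this stands and limits the likely harm. It does not correct a citation to an appendix that lacks the cited content.

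On rash, 5.2.1 can be read as self-care and 5.6 as what staff say when a rash is reported. A participant who follows 5.2.1 calls after both ointments have been tried, and the sections then agree. That stands too, so the conflict is confined to a rash reported untreated. No harm from either order is shown.

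The diarrhea triggers differ in kind and can be followed together, so they are not contradictory. The sheet nevertheless omits the stool count.

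No section expressly says that Appendix B holds loperamide directions. Section 5.6 only hands the sheet out directly after giving them. The evidence for loperamide comes from weekly doses of 1200 to 2000 mg, above the 600 mg used here.

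**Conclusion.** The concern holds. The citation of Appendix B for ointment instructions is wrong as written, and 5.2.1 and 5.6 conflict for a rash reported before clindamycin is tried (2 against 4 applications a day). The sheet carries 0 of 3 self-treatment directions and lacks the 3-4 stools a day call trigger. For a participant relying on it alone, a call about frequent first-day diarrhea could come up to, but less than, 24 hours later than 5.2.1 intends, or not be prompted at all. The 18-hour and 12-hour examples rest on assumed onset times. How many participants would be affected is unknown.

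This is a minor participant-safety inconsistency. It has no bearing on sample size, power or the primary analysis, but it should be corrected because participants are meant to be given this sheet.

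**What to change.** - Use one ointment sequence in 5.2.1 and 5.6. The stepwise one in 5.2.1 would serve: clindamycin first, hydrocortisone added if lesions do not improve, applied two hours apart. The investigators should also state how long to wait before judging improvement, since 5.2.1 gives no interval.
- Add the clindamycin, hydrocortisone and loperamide directions to Appendix B.
- Have Appendix B tell participants to call at 3-4 watery stools a day, or for rash or diarrhea lasting over 24 hours, whichever comes first, and use the same call rules in 5.2.1.

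The cost is amendment wording and a revised participant sheet, with no new visit, procedure, data item or analysis.
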